13.6.2 Overdose

An overdose is defined as a subject receiving a dose of IMP in excess of that specified in this protocol. The term ‘overdose’ including a specification of why it occurred (accidental or intentional) must be documented on the AE form of the eCRF. In addition, AEs originating

from overdose must be documented on a separate line. If the AE originating from the overdose qualifies as an SAE, expedited reporting is required (Section 13.4).

LEO does not recommend specific treatment for an overdose. The investigator will use clinical judgement to treat any overdose if necessary.

13.6.3 Medication error

Medication error refers to any unintentional error in the dispensing or administration of an IMP while in the control of the investigator or subject. Broadly, medication errors fall into 4 categories: wrong medication, wrong dose (including strength, form, concentration, amount), wrong route of administration, or wrong subject.

The medication error category must be documented on the AE form in the eCRF. In addition, AEs originating from a medication error must be documented on a separate line. If the AE originating from the medication error qualifies as an SAE, expedited reporting is required (Section 13.4). If the medication error is due to a device deficiency, the device deficiency must be reported as a product complaint as described in Section 9.10.

13.6.4 Misuse

Misuse refers to situations where the IMP is intentionally and inappropriately used not in accordance with the protocol. The term ‘misuse’ must be documented on the AE form in the eCRF. In addition, AEs originating from misuse must be documented on a separate line. If the AE originating from misuse qualifies as an SAE, expedited reporting is required (Section 13.4).

13.6.5 Abuse

Abuse relates to the sporadic or persistent, intentional excessive use of an IMP which is accompanied by harmful physical or psychological effects.

The term ‘abuse’ must be documented on the AE form in the eCRF. In addition, AEs originating from abuse must be documented on a separate line. If the AE originating from abuse qualifies as an SAE, expedited reporting is required (Section 13.4).

13.6.6 Aggravation of condition

Any clinically significant aggravation/exacerbation/worsening of any medical condition(s), compared to screening must be reported as an AE. If the AE originating from aggravation of a condition qualifies as an SAE, expedited reporting is required (Section 13.4).

13.7 Follow-up for final outcome of adverse events

During the trial, the investigator should follow up for final outcome on all AEs (including SAEs). Once a subject leaves the clinical trial, the investigator should follow up on the outcome of all non-serious AEs classified as of possible/probable relationship to the IMP for 2 weeks or until the final outcome is determined, whichever comes first.

SAEs must be followed up until a final outcome has been established, that is, the follow-up may continue beyond the end of the clinical trial. For SAEs which have stabilised and cannot be expected to recover during the trial or the safety follow-up periods, for example chronic or stabilised conditions, 'not recovered' should be reported as a final outcome. In addition, a statement that the SAE has stabilised or is chronic should be added to the narrative description of the SAE on the SAE form.

13.8 Handling of an urgent safety measure

An urgent safety measure is a measure taken to implement an action/protocol deviation under an emergency. This is defined as “...*the occurrence of any new event relating to the conduct of the trial or the development of the investigational medicinal product where that new event is likely to affect the safety of the subjects, the sponsor and the investigator shall take appropriate urgent safety measures to protect the subjects against any immediate hazard.*” (36).

If the investigator becomes aware of information that necessitates an immediate change in the clinical trial procedure or a temporary halt to the clinical trial in order to protect clinical trial subjects from any immediate hazard to their health and safety, the investigator can do so without prior approval from LEO, regulatory authorities, or IRBs/IECs.

The investigator must immediately inform LEO – by contacting the clinical project manager or medical expert – of this change in the clinical trial procedure or of the temporary halt providing full details of the information and the decision-making process leading to the implementation of the urgent safety measure.

LEO must act immediately upon receipt of the urgent safety measure notification in accordance with internal procedures and local legislation.

14 Statistical methods

14.1 Sample size

With a significance level of 5%, a sample size of 250 subjects will provide 99% power for detecting a treatment difference for the primary endpoint, assuming an EASI75 response rate at Week 16 of 40% vs 15% for tralokinumab+TCS and placebo+TCS, respectively. Assuming a response rate of 30% vs 15% in reduction of Worst Daily Pruritus NRS (weekly average) score of at least 4 from baseline to Week 16 for tralokinumab+TCS and placebo+TCS, respectively, the trial will provide at least 80% power for rejecting the hypotheses related to the primary endpoint and the secondary endpoint evaluating pruritus at Week 16.

14.2 Trial analysis sets

All screened subjects will be accounted for in the CTR.

All subjects randomised to treatment and exposed to the IMP will be included in the full analysis set (FAS) and will be analysed for efficacy. Exclusions from the FAS can be considered in special cases as described in the ICH E9 guideline, Section 5.2.1 (37). If it is decided to exclude a randomised subject from the FAS, a justification addressing ICH E9 will be given.

The following safety analysis sets are applied:

- ‘safety analysis set’ for all subjects exposed to IMP within the treatment period.
- ‘safety follow-up analysis set’ for all subjects exposed to IMP within the safety follow-up period.

The decisions regarding inclusion/exclusion of subjects from the trial analysis sets will be documented in the analysis set definition document before breaking the randomisation code.

14.3 Statistical analysis

14.3.1 Aspects related to the COVID-19 pandemic

As the implications of the COVID-19 pandemic will, extraordinarily, influence trial events and data in manners not foreseen by the protocol, this section is introduced to elaborate on the COVID-19 pandemic related aspects that may require special handling depending on the original research question.

- **Permanent discontinuation of IMP due to the COVID-19 pandemic:**

In general, permanent discontinuation of IMP can be interpreted as lack of efficacy of IMP and is therefore in some of the pre-specified analyses in the original protocol used to conclude non-response of the relevant subject. This interpretation is not appropriate when permanent discontinuation of IMP is caused by an external circumstance related to the COVID-19 pandemic.

The causal relationship to the COVID-19 pandemic will be documented in the eCRF. The handling of permanent discontinuation of IMP will depend on whether it is due to the COVID-19 pandemic or not. The date of this event will be the date of permanent discontinuation of IMP.

- **Use of rescue treatment due to unavailability of IMP related to the COVID-19 pandemic:**

Analogous to the handling of permanent discontinuation of IMP, interpretation of rescue treatment as lack of efficacy of IMP is not appropriate if rescue treatment is administered to compensate for unavailability of IMP due to the COVID-19 pandemic. It is therefore likewise relevant to determine whether this is the case.

The collection of concomitant medication does not allow for directly linking rescue treatment to the COVID-19 pandemic. Instead, rescue treatment will be attributed to the COVID-19 pandemic if it is administered while IMP dosing is missing due to the COVID-19 pandemic or if it is given after permanent discontinuation of IMP due to the COVID-19 pandemic (these underlying conditions may both be fulfilled).

Hence, rescue treatment will be attributed to the COVID-19 pandemic if it is administered in a time period where IMP is unavailable due to the COVID-19 pandemic. Such periods can be one of the following:

1. From the date of a conducted scheduled visit without IMP dosing due to the COVID-19 pandemic until the date of the next administered dose.
2. From 3 days prior to the planned date of a scheduled visit which is not conducted due to the COVID-19 pandemic until the date of the next administered dose.
3. From the date of permanent discontinuation of IMP due to the COVID-19 pandemic.

The date of this event will be the date of the administration of rescue treatment.

- **Prolonged interruption of IMP dosing due to the COVID-19 pandemic:**

A temporary pause in dosing due to the COVID-19 pandemic may influence the interpretation of the subsequent outcome for the subject, and the event will therefore be reported.

At the first occurrence, for which a subject misses IMP doses in one of the 4 following scenarios, the subject will be defined as having a prolonged interruption of IMP due to the COVID-19 pandemic:

1. 3 consecutive missed IMP doses, for which at least one of them is due to the COVID-19 pandemic.
2. 2 consecutive missed IMP doses, for which at least one of them is due to the COVID-19 pandemic and the third consecutive IMP dose is delayed for more than 7 days beyond the planned date of the IMP dosing.
3. Week 22 and Week 24 IMP doses and the Week 26 visit are missed, for which at least one of them is due to the COVID-19 pandemic.
4. Week 22 and Week 24 IMP doses are missed, for which at least one of them is due to the COVID-19 pandemic, and the Week 26 visit is delayed for more than 7 days beyond the planned date.

In scenarios 1 and 3, the start date of the event will be the planned date of the third consecutive missed IMP dose or the Week 26 visit. In scenarios 2 and 4, the start date of the event will be the planned date of the third consecutive IMP dose +7 days or the Week 26 visit + 7 days.

- **Missing data due to the COVID-19 pandemic:**

The collection of data at planned visits allows to report if data is missing due to the COVID-19 pandemic, either due to the subject being prohibited from visiting the sites or the visit being performed via telephone/video, thereby only allowing for a subset of data to be collected.

In the context of some of the efficacy analyses, data recorded missing due to the COVID-19 pandemic will be handled differently from data missing for other reasons. As an example, it may not be reasonable to impute missing binary responder values as a non-response if the missingness is due to the COVID-19 pandemic.

It should be noted that a subject may have missing data due to the COVID-19 pandemic, even though the subject may not have discontinued IMP permanently or temporarily due

to the COVID-19 pandemic. This could e.g. be the case if the subject continue treatment with tralokinumab via home-use ([Appendix 8](#)).

- **Infection with COVID-19:**

Infection with COVID-19 as an AE may give rise to one of the scenarios described above but will not be handled differently from other types of AEs.

14.3.2 Disposition of subjects

For all randomised subjects the reasons for permanent discontinuation of IMP and for withdrawal from the trial will be presented by treatment group.

Permanent discontinuation of IMP due to the COVID-19 pandemic will be added to the list of reasons and identified based on the information documented in the eCRF.

14.3.3 Demographics and other baseline characteristics

Descriptive statistics of demographics and other baseline characteristics will be presented for all randomised subjects. The presentations will be overall and by treatment group.

Demographics (age, sex, race, and ethnicity) and baseline disease characteristics (IGA, EASI, SCORAD, DLQI, and Worst Daily Pruritus NRS score) will be presented by the stratification factors: prior CSA use (yes/no), country (Germany: yes/no), and baseline disease severity (IGA 3 or 4).

Other baseline characteristics include vital signs (including height, weight, body mass index), duration of AD, concurrent diagnoses (from medical history and indications for concomitant medication), concomitant medications, and previous AD treatments.

14.3.4 Exposure and treatment compliance

Exposure

Exposure to treatment will be presented for the safety analysis set as days of exposure per treatment group.

Treatment compliance

Compliance to treatment regimen will be recorded in the eCRF. If any complications or deviations in administration are observed, these will be described as protocol deviations. Treatment compliance will be presented for the total missed IMP doses, missed IMP doses not due to the COVID-19 pandemic, and the missed IMP doses due to the COVID-19 pandemic for the safety analysis set for each treatment group.

14.3.5 Rescue treatment

Rescue treatment will be defined by the following algorithm:

Concomitant medications with ‘Dermatitis atopic’ or ‘Dermatitis infected’ as the preferred term (PT) for the indication, and either of the following:

- ATC2 code H02
- Preferred name Methotrexate, Methotrexate sodium, Ciclosporin, Azathioprine, Mycophenolate-mofetil, Mycophenolate-acid, Mycophenolate-sodium, Dupilumab, Crisaborole, or Alitretinoin
- ATC4 code D07AD or D07BD or D07CD or D07XD
- Confirmed rescue treatment (by investigator) in reported term for the indication, and ATC4 code D07AB or D07BB or D07CB or D07XB or D07AC or D07BC or D07CC or D07XC

As described in Section 9.5, investigators should make every attempt to conduct efficacy and safety assessments immediately before administering any rescue treatment. Therefore, if rescue treatment has start date the same day as an efficacy assessment, then it is assumed that the assessment is not influenced by rescue treatment.

Rescue treatment will be summarised for the entire treatment period as well as for the period up until the Week 16 visit (actual or nominal). Rescue treatment will also be summarised for the periods prior to and after the start of the COVID-19 pandemic, within the treatment period. The start date(s) of the COVID-19 pandemic will be decided prior to unblinding in the statistical analysis plan, possibly reflecting on when trial procedures were disrupted on a national level.

Additionally, rescue treatment will be summarised for the entire treatment period by the variables: prior CSA use (yes/no), country (Germany: yes/no), and baseline disease severity (IGA 3 or 4).

A summary table of rescue treatment by type (topical and systemic) and by overall group (corticosteroids, immunosuppressants, and other) will be made for the entire treatment period as well as for the period up until the Week 16 visit (actual or nominal).

[figure not shown]
In addition, the time to first use of rescue treatment will be presented using Kaplan-Meier plots for the whole treatment period.

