8.3 Exclusion criteria

Subjects must not enter the trial if any of the following exclusion criteria are fulfilled:

1. Subjects for whom TCS are medically inadvisable e.g., due to important side effects or safety risks (including intolerance to treatment, hypersensitivity reactions, significant skin atrophy, systemic effects etc.) in the opinion of the investigator.
2. Concurrent enrolment in another interventional clinical trial.

3. Previous randomisation in a tralokinumab clinical trial.
4. Active dermatologic conditions that may confound the diagnosis of AD or would interfere with assessment of treatment, such as scabies, cutaneous lymphoma, or psoriasis.
5. Known active allergic or irritant contact dermatitis that is likely to interfere with the assessment of severity of AD.
6. Use of tanning beds or phototherapy (narrow band ultraviolet B [NBUVB], ultraviolet B [UVB], ultraviolet A1 [UVA1], psoralen + ultraviolet A [PUVA]), within 6 weeks prior to randomisation.
7. Treatment with the following medications within 4 weeks prior to randomisation:
 - Systemic immunosuppressive/immunomodulating drugs (e.g. methotrexate, CSA, azathioprine, mycophenolate mofetil, Janus kinase inhibitors).
 - Systemic corticosteroid use (excludes topical, inhaled, or intranasal delivery).
 - Three or more bleach baths during any week within the 4 weeks.
8. Treatment with topical PDE-4 inhibitor within 2 weeks prior to randomisation.
9. Receipt of live attenuated vaccines within 30 days prior to the date of randomisation and during the trial including the safety follow-up period.
 - Receipt of inactive/killed vaccinations (e.g. inactive influenza) is allowed, provided they are not administered within 5 days before/after any trial visit.
10. Receipt of any marketed biological therapy (i.e. immunoglobulin, anti-IgE) including dupilumab or investigational biologic agents:
 - Any cell-depleting agents including but not limited to rituximab: within 6 months prior to randomisation, or until lymphocyte count returns to normal, whichever is longer.
 - Other biologics: within 3 months or 5 half-lives, whichever is longer, prior to randomisation.
11. Receipt of any investigational non-biologic agent within 5 half-lives prior to randomisation.
12. Receipt of blood products within 4 weeks prior to screening.

13. Major surgery within 8 weeks prior to screening, or planned in-patient surgery or hospitalisation during the trial period.

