9.5 Rescue treatment

If medically necessary (i.e., to control intolerable AD symptoms), rescue treatment for AD may be provided to trial subjects at the discretion of the investigator. If possible, investigators should attempt to limit the first step of rescue therapy to topical medications (i.e. higher potency TCS, Europe class >3), and escalate to systemic medications only for subjects who do not respond adequately after at least 14 days of topical treatment. The subject will be monitored for signs of local or systemic TCS toxicity and the safety and appropriateness of continued use will be supervised by site staff.

Subjects who receive topical rescue treatment (higher potency TCS, Europe class >3) will continue IMP treatment.

If a subject receives rescue treatment with systemic corticosteroids or non-steroidal systemic immunosuppressive drugs (methotrexate, mycophenolate mofetil, azathioprine, etc.), IMP will be immediately discontinued (see Section 10.2.2). After the treatment with these medications is completed, IMP may be resumed if deemed appropriate by the investigator, but not sooner than 5 half-lives after the last dose of systemic rescue treatment. The use of biological rescue treatment will be disallowed for the entire trial duration.

Investigators should make every attempt to conduct efficacy and safety assessments (at least disease severity scores [IGA and EASI], concomitant medications/ procedures, and AEs) immediately before administering any rescue treatment. An unscheduled visit may be used for this purpose, if necessary. In the primary efficacy analyses, subjects who receive higher potency TCS (Europe Class >3) or systemic rescue treatment during the treatment period will be considered as non-responders.

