9.7 Prohibited medication and procedures

The medications listed below are prohibited during the trial from randomisation. Medications and procedures disallowed prior to randomisation are covered in the exclusion criteria (see Section 8.3). In case any prohibited treatments are used during the trial, they must be recorded as concomitant medication.

From randomisation through end of treatment (Week 26):

- PDE-4 inhibitors.
- TCS of higher potency (Europe class >3).
- Use of UVA or UVB, psoralen + UVA (PUVA), other phototherapy, or tanning beds.
- 3 or more bleach baths per week.

From randomisation through safety follow-up (Week 40):

- Investigational agents other than tralokinumab.

- Systemic corticosteroids (nasal and inhaled corticosteroids are allowed).
- Systemic treatment for AD with an immunosuppressive/immunomodulating agent (examples include: cyclosporine A, mycophenolate mofetil, azathioprine, methotrexate, Janus kinase inhibitors, interferon-gamma, dupilumab, or other biologics).

In case prohibited systemic medications are received (for any indication), IMP dosing must be suspended as described in Section 10.2.2.

The sponsor's medical expert must be notified if a subject receives any of the following prohibited medications from randomisation through safety-follow-up (Week 40):

- Allergen immunotherapy.
- Live (attenuated) vaccine.
- Immunoglobulins.
- Blood products.

The sponsor's medical expert will determine whether IMP discontinuation is required. Please note that receipt of inactive/killed vaccines (e.g. inactive influenza) is allowed, provided they are not administered within 5 days before/after any trial visit.

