10.2.2 Reasons for temporary discontinuation of IMP

IMP dosing may be temporarily suspended in the event of:

- Other intercurrent illnesses or major surgery.
- An infection that requires parenteral treatment with antibiotic, antifungal, antiviral, anti-parasitic, or anti-protozoal agents.
- Treatment with systemic corticosteroids or non-steroidal immunosuppressive/immunomodulating medications (e.g., methotrexate, azathioprine, mycophenolate mofetil, Janus kinase inhibitors, biologic agents). After the treatment with these medications is completed, IMP may be resumed if deemed appropriate by the investigator, but not sooner than 5 half-lives after the last dose of systemic therapy.

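### The closed rescue-treatment algorithm does not flag a systemic Janus kinase inhibitor given for atopic dermatitis, so an observed EASI75 response after one could count as response in the primary estimand

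*Protocol*

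**What the plan says.** **The algorithm.** Protocol 14.3.5 identifies rescue from concomitant medications coded to an atopic or infected dermatitis indication that also meet one of four conditions: ATC2 code H02; one of ten names ("Preferred name Methotrexate, Methotrexate sodium, Ciclosporin, Azathioprine, Mycophenolate-mofetil, Mycophenolate-acid, Mycophenolate-sodium, Dupilumab, Crisaborole, or Alitretinoin"); certain D07 codes; or other D07 codes that the investigator confirmed as rescue. SAP 6.5 keeps this definition and adds only an exception for potent topical corticosteroid (TCS) use that ends on the day of randomisation.

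**The clinical rule.** Protocol 9.5 describes non-steroidal systemic rescue as "non-steroidal systemic immunosuppressive drugs (methotrexate, mycophenolate mofetil, azathioprine, etc", which is an open class. It states that subjects with higher-potency TCS or "systemic rescue treatment during the treatment period will be considered as non-responders" in the primary efficacy analyses. On biologics it says: "The use of biological rescue treatment will be disallowed for the entire trial duration".

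**Where Janus kinase inhibitors appear.** Exclusion criterion 7 lists them: "Systemic immunosuppressive/immunomodulating drugs (e.g. methotrexate, CSA, azathioprine, mycophenolate mofetil, Janus kinase inhibitors". Section 9.7 prohibits them as systemic treatment for atopic dermatitis: "azathioprine, methotrexate, Janus kinase inhibitors, interferon-gamma, dupilumab, or other biologics". Section 10.2.2 lists them among reasons to suspend dosing temporarily: "azathioprine, mycophenolate mofetil, Janus kinase inhibitors, biologic agents". After that, "IMP may be resumed if deemed appropriate by the investigator, but not sooner than 5 half-lives after the last dose of systemic therapy".

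**What decides response.** Section 14.3.7 and SAP 6.8.5 recognise three intercurrent events: rescue treatment, permanent discontinuation of IMP, and COVID-19 subject-onset. With none of these before the visit, Panel 13 and SAP Table 9 use the observed value.

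**The concern.** The primary estimand (14.3.8.1) counts only responses reached without any rescue, so the rescue flag is part of the outcome definition. If a drug is rescue under 9.5 but not under 14.3.5, the two sections can classify the same subject differently, and the programmed analysis will follow 14.3.5.

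A Janus kinase inhibitor given for atopic dermatitis is such a drug. Because 10.2.2 provides for temporary suspension of IMP, its use need not lead to permanent discontinuation, which would otherwise make the subject a non-responder. Prohibited medication is not itself an intercurrent event.

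The same flag serves the composite estimand and the binary secondary endpoints. It also decides which SCORAD and DLQI data are dropped from the hypothetical analysis (14.3.9.1). The treatment policy estimand ignores rescue and is not affected.

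**Working it through.** **Step 1: compare the lists**

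| Agent | 9.5 | Criterion 7 | 9.7 | 10.2.2 | 14.3.5 flags it |
|---|---|---|---|---|---|
| Methotrexate, azathioprine, mycophenolate | named | named | named | named | yes |
| Janus kinase inhibitors | only through the open class | named | named | named | **no** |
| Dupilumab | disallowed, as a biologic | not named | named | as a biologic | yes |
| Interferon-gamma | not named | not named | named | not named | no |
| Other biologics | disallowed | not named | as a class | as a class | no |

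One premise is an assumption, because the documents do not define the ATC codes: H02 and D07 are taken to be systemic and topical corticosteroid codes, so a Janus kinase inhibitor falls in neither. The investigator-confirmed route also requires a D07 code, so it does not catch systemic drugs.

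**Step 2: conditions for misclassification.** All of these must hold for a subject given the drug for atopic dermatitis before Week 16:

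1. No flagged rescue came before the Week 16 visit.
2. IMP was not permanently discontinued before Week 16.
3. There was no COVID-19 subject-onset.
4. The subject stays in the full analysis set.
5. The Week 16 EASI was observed and meets EASI75.

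A user with an observed non-response is classified the same way under either section.

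**Step 3: reproduce the plan's power.** Inputs are from 14.1, 7.1 and 14.3.16: 250 subjects randomised 1:1, so n = 125 per arm; rates 40% and 15%; two-sided 5%.

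Power = Φ{[d − 1.96·√(2p̄(1−p̄)/n)] / √[(p₁(1−p₁) + p₀(1−p₀))/n]}

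With d = 0.25 and p̄ = 0.275:

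- null term: 1.96 × √(2 × 0.275 × 0.725/125) = 0.1107
- denominator: √[(0.24 + 0.1275)/125] = 0.0542
- power: Φ(0.1393/0.0542) = Φ(2.57) = 99.5%, against the stated 99%

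**Step 4: size of the effect.** With m users in an arm, of whom a share r have an observed EASI75 response, the arm shifts by 100·m·r/125 points. Both m and r are assumptions; the documents give neither.

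| m | r = 15% | r = 40% | r = 100% |
|---|---|---|---|
| 1 | 0.12 | 0.32 | 0.80 |
| 3 | 0.36 | 0.96 | 2.40 |

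Effect of three users on the planning difference:

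| Arm and r | Placebo rate | Tralokinumab rate | Difference (points) | Power |
|---|---|---|---|---|
| No users | 15.00% | 40.0% | 25.0 | 99.5% |
| Placebo, 15% | 15.36% | 40.0% | 24.64 | 99.4% |
| Placebo, 40% | 15.96% | 40.0% | 24.04 | 99.1% |
| Placebo, 100% | 17.40% | 40.0% | 22.6 | 98.0% |
| Tralokinumab, 100% | 15.00% | 42.4% | 27.4 | 99.85% |

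Placebo users bias against tralokinumab; tralokinumab users bias in its favour.

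**The case against.** **Topical treatment comes first.** Section 9.5 asks that rescue begin, where feasible, with higher-potency TCS, and that systemic drugs follow only after at least 14 days without adequate response. The algorithm flags higher-potency TCS, so a subject who follows that sequence would normally be a non-responder before any systemic drug starts. This stands and narrows the path considerably. It does not close it, because the sequence is a request and not a requirement.

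**The conflict with 9.5 is not express.** Every non-steroidal drug that 9.5 names is in the algorithm. Janus kinase inhibitors enter through the open wording, read with lists whose class (immunosuppressive or immunomodulating) is somewhat wider. That is fair. The reading is still the natural one, since 9.5 refers to 10.2.2 for these drugs and 10.2.2 names Janus kinase inhibitors alongside them.

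**The drugs are prohibited, so use is only a deviation.** This does not explain the gap. The algorithm lists dupilumab, although 9.5 disallows biological rescue, and ciclosporin, although 9.7 prohibits it. The list already covers drugs that should not have been given.

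**Blinded review would find such a case.** It may: 9.7 requires prohibited drugs to be recorded, 14.3.16 requires review of the analyses against blinded data, and SAP 5 reviews critical deviations. None of these prescribes non-response, and the SAP 5 review can only keep or remove the subject.

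**A stronger reading about other agents.** A reader might infer that the omission of interferon-gamma and of biologics other than dupilumab is an equal contradiction. The documents do not support that. Section 9.5 does not name interferon-gamma and disallows biological rescue outright, so for these agents the conflict is only inferred, by reading 9.5 with 9.7.

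**Conclusion.** The point holds as a minor, conditional gap. The operational definition of rescue is narrower than the rule in 9.5, and it can count as response an outcome that the primary estimand says should not count. The discrepancy lies in the definition itself, so it exists whether or not any subject is affected.

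A reader might infer that every response after such a drug will be miscounted, or that the primary result is in doubt. Neither follows. All five conditions in the working must hold together, and the topical-first sequence would already have flagged most subjects who follow it. The documents show no user of any of these drugs. Each responding user shifts an arm by 0.8 points. In the most adverse of the assumed cases, three placebo users who all respond, planning power falls from 99.5% to 98.0%. The primary conclusion is unlikely to change.

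This rests on reading the open class in 9.5 to include Janus kinase inhibitors, on the assumed scope of H02 and D07, and on use being rare.

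**What to change.** Before unblinding, add one criterion to Protocol 14.3.5 and SAP 6.5: any systemic immunosuppressive or immunomodulating agent with an atopic dermatitis indication, naming Janus kinase inhibitors, is rescue treatment in addition to the existing conditions. Confirm the flag by blinded review of a listing of concomitant medications with that indication.

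Since dupilumab is already listed, the same criterion may for consistency cover the other systemic agents in 9.7 (interferon-gamma and other biologics).

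The cost is one added criterion and one blinded listing review. The medications are already recorded, so no new data are needed, and the sample size does not change.
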